7.3.8 Contraceptive Counseling

All study participants (male and female) will be counseled on the use of effective forms of birth during study participation and in the 30 days following the final study visit. If a pregnancy occurs during this time period (in either the subject or the subject's partner), the participant will be asked to inform the study team immediately.

7.3.9 Suicidality: Columbia Suicide Severity Rating Scale (C-SSRS)

The C-SSRS is a suicidal ideation rating scale to evaluate suicidality. It rates an individual's degree of suicidal ideation on a scale, ranging from "wish to be dead" to "active suicidal ideation with specific plan and intent"⁴⁷. The C-SSRS will be administered by trained raters at specified time points, as indicated in Table 3 as well as when clinically indicated. Any subjects demonstrating evidence of suicidality will prompt

immediate consultation with the site's on-call psychiatrist for assistance with decision-making and potential referral to behavioral health services.

7.3.10 Nasal Irritation Scale

Study team will ask subjects if they are experiencing any nasal irritation (schedule see Table 3) on a Likert scale of 0-10, with 0 being no irritation and 10 being severe irritation. The scale will be administered 5 times at the following predetermined intervals: Once immediately before study drug administration, and again at 20 and 40 minutes post-administration. Research staff will also observe whether the subject has experienced any bleeding (Yes/No). If Yes, they will be asked to categorized the bleeding as: a) Bleeding which stops within 1 minute; b) Bleeding, taking 1-5 minutes to stop; c) Bleeding for 4-60 minutes, does not require medical intervention; d) Bleeding which requires medical intervention.

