4.3 Safety

- Incidence and severity of serious adverse events (SAEs) and adverse events (AEs)
- Frequency of change in clinically-significant vital signs
- fingerstick glucose level <70mg/dl

5 Study Design

This Phase 1 is a single center, open-label, randomized pharmacokinetic study designed to describe the central nervous system delivery of intranasal insulin to CSF using anIN delivery device.

Table 1: Study Design

INI Insulin Dose	Collection Times
40 IU (n=6) 2 x 200 μ L (0.2ml)	0, 10, 20, 30, 40 min
80 IU (n=6) 2 x 200 μ L (0.2ml) Wait 2 min 2 x 200 μ L (0.2ml)	0, 10, 20, 30, 40 min

After written informed consent has been obtained, subjects will be screened to assess study eligibility based on study inclusion/exclusion criteria. Subjects who are eligible at the end of the screening visit will be randomized and assessed for outcome measures, including lumbar puncture and CSF/blood draw following a single dose of INI administered by the trained research staff. Randomization will be stratified by gender to ensure a balanced distribution of male and female participants within each group. A Block randomization scheme will be employed to ensure that the final group sizes are equivalent.

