7.1.2.1 Fluoroscopy-Guided Lumbar Puncture Procedure

CSF samples will be collected according to standard operating procedures for fluoroscopy-guided lumbar puncture as observed by the General Radiology department at Regions Hospital. The procedure will be performed by a trained clinician (i.e., an interventional radiologist or an experienced member of their team), who will obtain verbal consent (in addition to the research informed consent obtained/documentated at Visit 1). CSF will be collected serially using gravity drainage. Sterile extension tubing connected to the LP needle will dispense CSF into sterile collection tubes for pharmacokinetic analysis. Samples will be collected at 5 times: once prior to the administration of a single dose of intranasal insulin and at once each at 10, 20, 30, and 40 minutes post-drug administration. Approximately 1-2ccs of CSF will be collect at all 5 time points for a total of 10ccs of CSF. The tubing connected to the needle will be flushed out between sample collections to avoid contamination between specimen timepoints. The subject will lie in prone position throughout the procedure with appropriate measures taken to minimize discomfort (e.g., provision of warm blankets, use of positioning sponges, etc.).

Subjects will lie on their back 2 hours after the procedure for standard-of-care monitoring with nursing staff, and periodic collection of vital signs. Participants will receive instructions from the clinical team on techniques for preventing and treating post-LP headache (e.g., drinking water and caffeinated beverages, using over-the-counter pain medications). They will also receive guidance on when to seek additional help for their headache and/or any other emergent symptoms requiring immediate medical attention such as fever, persistent headache, and weakness/numbness of the lower extremities. Subjects will receive a safety assessment phone call from study staff 1 day after the procedure.

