7.3.11.2 Serum Samples

It is our intention to collect samples at pre-defined times following a single dose administration. Serum will be collected at 0, 10, 20, 30 and 40 minutes for all study participants. Serum samples will be assessed for insulin using the same one-step sandwich immunoassay with a limit of detection of 0.1 µIU/ml or 0.7 pmol/L.

Table 2: Study Visit Schedule

Assessment/ Procedure	Visit 1: Screen	Visit 2: Lumbar Puncture (LP)	Phone Visit 1: Safety Check	Follow-up Visit 3	Ad Hoc Visit if Symptomatic
Schedule – Week and Windows	-2	1	Following day after LP	Within 1 week of Visit 2	
		± 7 days	+ 1 day	± 5 days	
Informed consent	X				
Review of inclusion/exclusion criteria	X	X			
Medical History, demographics	X				
Physical/Neuro exam with examination of nares and nasal passages	X			X	X
Vital Signs (Blood pressure, heart rate, weight)	X	X		X	X
Height	X				

Basic Metabolic Panel (Na, K, CO ₂ , CL, BUN, Creatinine, Glucose and Ca)	X			X	
Labs INR/PT/PTT	X			X	
Complete Blood Count	X			X	
Pregnancy Test (in females)	X	X		X	
Counseling on effective birth control	X	X		X	
Randomization		X			
Lumbar Puncture		X			
Glucose Finger Stick (0 Min, 15 Min, 45 Min)		X			
Nasal Irritation Scale (0, 20, 40 min)		X			
CSF Samples and Insulin Levels (0-40 Min)		X			
Serum insulin Levels (0-40 Min)		X			
C-SSRS, 12-Lead Standard ECG	X			X	
Pre-Procedure instructions	X				
Study Drug Administration (single dose)		X			
Concomitant Medication	X	X	X	X	X
Adverse Events	X	X	X	X	X

8 Investigational Product(s)

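### The nasal bleeding categories in section 7.3.10 are neither mutually exclusive nor exhaustive; the effect is confined to the descriptive record of bleeding severity

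*Combined protocol and SAP*

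**What the plan says.** Section 7.3.10 has staff note whether bleeding occurred, as a Yes/No item, and then has each bleed sorted into one of four categories:

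- Category a is for a bleed that is over inside one minute, with intervention not mentioned.
- Category b reads "Bleeding, taking 1-5 minutes to stop", again with intervention not mentioned.
- Category c reads "Bleeding for 4-60 minutes, does not require medical intervention", so it alone joins a duration to a condition on intervention.
- Category d is for any bleed that needs intervention, with no duration given.

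The section gives no rule for a bleed that meets two descriptions, no residual category, and no instruction to record the duration itself. The study visit schedule gives the times of the nasal irritation scale (0, 20 and 40 minutes) and does not restate the bleeding categories. On observation after the procedure, section 7.1.2.1 says: "Subjects will lie on their back 2 hours after the procedure for standard-of-care monitoring with nursing staff".

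Section 4.3 lists the incidence and severity of adverse events as a safety endpoint. Section 12.2 plans a descriptive summary of adverse events by group.

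**The concern.** A coding list should give every event exactly one code. This list mixes two criteria, duration and need for intervention, without applying both to every category, and two of its duration ranges overlap. Two people following the text could code the same 4 to 5 minute bleed differently, and both would be right. Because the text does not ask for the duration, the ambiguity might not be resolvable afterwards.

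What is at stake is whether the descriptive account of bleeding severity by dose group can be read without doubt. In an arm of six, one bleed coded differently moves a category count by 1/6, about 17% of the arm.

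**Working it through.** No sample size, power or error rate enters here. The check is to code the four categories as written and see which ones each bleed satisfies.

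**Inputs (section 7.3.10), with t the duration in minutes and range ends included**

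- a: t ≤ 1; intervention not mentioned
- b: 1 ≤ t ≤ 5; intervention not mentioned
- c: 4 ≤ t ≤ 60, and no intervention
- d: intervention required, any t

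**Result**

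| Duration (min) | No intervention | Intervention required |
|---|---|---|
| 0.5 | a | a, d |
| 1 | a, b | a, b, d |
| 3 | b | b, d |
| 4, 4.5, 5 | b, c | b, d |
| 5.5, 30, 60 | c | d |
| 60.5, 61, 90, 120 | none | d |

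There are four faults:

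1. From 4 to 5 minutes without intervention, both b and c apply.
2. Over 60 minutes without intervention, no category applies.
3. At exactly 1 minute, both a and b apply.
4. At 5 minutes or less with intervention, a or b applies as well as d.

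**Dependence on the range ends.** Only the third fault, and the exact points 4 and 5 in the first, depend on including the ends. If the ends are excluded, durations strictly between 4 and 5 minutes still fit b and c, durations over 60 still fit nothing, and a short bleed needing intervention still fits two categories.

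**If the 4 is a slip for 5.** Category c becomes 5 ≤ t ≤ 60. The overlap from 4 to just under 5 minutes goes. Exactly 5 minutes still fits b and c, and the second, third and fourth faults are unchanged.

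**Can the gap occur?** The last scheduled scale time is 40 minutes after dosing, so a bleed that starts after dosing has lasted at most 40 minutes by then. A bleed beyond 60 minutes could be seen only later, for example during the 2 hours of monitoring in section 7.1.2.1.

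**What uses the categories?** Section 4.3 does not name bleeding category as an endpoint. Section 12.2 summarises adverse events and does not mention the categories. The stopping criteria in section 13.2.1 rest on glucose readings and symptoms of hypoglycaemia. Section 7.3 has any clinically significant change recorded as an adverse event, whatever its category under 7.3.10.

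**The case against.** The strongest reply is that this is a drafting slip with almost no consequence. The 4 may well have been meant as 5. Few bleeds are likely in 12 participants, and a bleed over an hour with no intervention is remote. Section 1.1.3 names short-lived local irritation as the most common side effect, and irritation has its own 0 to 10 scale without overlapping categories. The case report form, which section 13.7 says is developed internally, is not in the documents, so it may already be right. Most of this stands and limits the weight of the point. It does not remove it: the documents do not say which digit was intended, changing it leaves three of the four faults, and 7.3.10 is the only statement of the categories available.

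A reader might infer more than the text supports:

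- **That one bleed could receive two categories or none.** No single bleed does both. Two categories and no category apply to different bleeds.
- **That adverse event incidence, or a comparison of local tolerability between the doses, is compromised.** A bleed of any length is still recorded as Yes and, if clinically significant, as an adverse event. The documents plan no comparison of bleeding categories and do not tie adverse event severity to them.
- **That a quarter of category b bleeds would be miscoded.** The overlap is (5 − 4)/(5 − 1) = 25% of the width of b. That is a ratio of range widths; the documents give no distribution of durations that would turn it into a miscoding rate.

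**Conclusion.** The coding rule in 7.3.10 is wrong as written, and the point is minor. The overlap between b and c and the absence of a category above 60 minutes without intervention follow directly from the wording. The overlap of a and b with d follows because a and b say nothing about intervention. The shared point at 1 minute assumes that range ends are included.

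The effect is limited to the descriptive record of bleeding severity, at most one category count per ambiguous bleed in an arm of six. For a bleed over 60 minutes without intervention, the event itself is still captured and only its category is missing. The primary and secondary endpoints, adverse event incidence and the stopping criteria are untouched. The conclusion assumes that the case report form follows 7.3.10; if it already uses clean categories, only the protocol text needs correcting.

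**What to change.** Before data collection, replace the four categories in 7.3.10 and on the case report form with:

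1. no medical intervention, up to 1 minute;
2. no medical intervention, over 1 and up to 5 minutes;
3. no medical intervention, over 5 minutes, with no upper limit;
4. medical intervention required, any duration.

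Record the duration in minutes alongside the category. Every row of the table above then receives exactly one code: without intervention, 0.5 and 1 minute fall in the first band, 3 to 5 minutes in the second, and 5.5 minutes and longer in the third; every bleed needing intervention falls in the fourth.

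The cost is a short edit to one section and one extra field on the form. It alters how a bleed is coded and leaves open when or how a bleed is treated, so clinical management does not change.

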7.3.11 Pharmacokinetic Sampling

The study team will attempt to collect the CSF and serum samples as close in time as possible for each PK time point. Given differences in how serum/CSF are extracted for this study, there may be a slight difference between collection start and stop times. To ensure consistency across participants, the study team will initiate collection of the CSF samples first, followed by the serum samples, at each of the 5 PK time points.

7.3.11.1 CSF Sampling

It is our intention to collect samples at pre-defined times following a single dose administration. CSF will be collected at 0, 10, 20, 30 and 40 minutes for all study participants. CSF samples will be assessed for insulin using a one-step sandwich immunoassay with a limit of detection of 0.1 µIU/ml or 0.7 pmol/L

7.3.11.2 Serum Samples

It is our intention to collect samples at pre-defined times following a single dose administration. Serum will be collected at 0, 10, 20, 30 and 40 minutes for all study participants. Serum samples will be assessed for insulin using the same one-step sandwich immunoassay with a limit of detection of 0.1 µIU/ml or 0.7 pmol/L.

Table 2: Study Visit Schedule

Assessment/ Procedure	Visit 1: Screen	Visit 2: Lumbar Puncture (LP)	Phone Visit 1: Safety Check	Follow-up Visit 3	Ad Hoc Visit if Symptomatic
Schedule – Week and Windows	-2	1	Following day after LP	Within 1 week of Visit 2	
		± 7 days	+ 1 day	± 5 days	
Informed consent	X				
Review of inclusion/exclusion criteria	X	X			
Medical History, demographics	X				
Physical/Neuro exam with examination of nares and nasal passages	X			X	X
Vital Signs (Blood pressure, heart rate, weight)	X	X		X	X
Height	X				

Basic Metabolic Panel (Na, K, CO ₂ , CL, BUN, Creatinine, Glucose and Ca)	X			X	
Labs INR/PT/PTT	X			X	
Complete Blood Count	X			X	
Pregnancy Test (in females)	X	X		X	
Counseling on effective birth control	X	X		X	
Randomization		X			
Lumbar Puncture		X			
Glucose Finger Stick (0 Min, 15 Min, 45 Min)		X			
Nasal Irritation Scale (0, 20, 40 min)		X			
CSF Samples and Insulin Levels (0-40 Min)		X			
Serum insulin Levels (0-40 Min)		X			
C-SSRS, 12-Lead Standard ECG	X			X	
Pre-Procedure instructions	X				
Study Drug Administration (single dose)		X			
Concomitant Medication	X	X	X	X	X
Adverse Events	X	X	X	X	X

8 Investigational Product(s)

8.1 Description of Investigational Product

The research staff will utilize the following investigational products:

- Intranasal delivery route
- Regular insulin (Novolin-R –U-100; Insulin Full Prescribing Information; Appendix C)
- SipNose Device

8.2 Handling and Storage

The study drug will be kept at study site per label recommendations and institutional Standard Operational Policy, specifically, but not limited to temperature controlled secure area.

To ensure that a stable temperature and/or conditions are maintained, site staff will verify and document temperature at a minimum of three times per week or monitored continuously if automated systems such as TempTrak are used. An electronic log will be securely stored at the study site. Study staff will be responsible for safeguarding and maintaining the master log.

8.3 Packaging and Labeling

Only designated study staff will be responsible for handling all investigational drug and devices; study participants will not be preparing/administering the drug themselves. The study drug will not be individually labeled; the study team may use the same vial of insulin for multiple participants in order to minimize waste.

All study drug will be labeled according to the following specifications:

- Protocol identifier/IRB approval/account/study number

- Quantity statement
- “Caution: New Drug—Limited by Federal (or United States) law to investigational use”

All study devices will be individually packaged and labeled by the manufacturer as follows:

REDACTED

8.4 Occupational Safety

No known significant safety risks exist to site personnel in direct or indirect contact with the study drug. As the lumbar puncture will employ fluoroscopy, clinical (non-research) staff will be exposed to radiation. The fluoroscopy technicians and radiologist will follow standard clinical protocols for radiation safety (e.g. wearing lead Personal Protective Garments). The amount/duration of radiation exposure for this research LP is not greater than what would be experienced during a routine LP. As fluoroscopy is only needed to assist with needle placement, study staff will not need to be present for this part of the procedure and can step out of the procedure room while the fluoroscopy machine is in use. Research staff can then reenter the room to assist with pre-dose sample collection/fingerstick glucose testing after the machine has been deactivated.

9 Concomitant Medications and Non-Drug Therapies

9.1 Permitted Medications

Any medication not listed in list of Prohibited Medications (Table 4) will be permitted during this study. A record will be kept by site staff detailing doses and indication of any concomitant medications used by subjects.

9.2 Prohibited Medications

Any subject with insulin-dependent diabetes taking insulin will be excluded from the study. Additional medications that are exclusionary and/or should be avoided during the study period are outline below in Table 4.

Table 3: Prohibited Medications

Prohibited Medications
Barbiturates
Benzodiazepines
Insulin
Muscle Relaxants
Opioids
Beta Blockers

10 Subject Completion and Withdrawal

10.1 Subject Completion

Subjects completing all study visits (4) will be considered to have completed study.

10.2 Subject Withdrawal

Subject may withdraw from study at any time for any reason without penalty or be terminated from the study by the clinical investigator (see provisions for termination by study team.) Investigational team will

document the reason(s) for withdrawal. In the event a subject chooses to withdraw from study before Visit 3, the safety procedures described in 7.3 will be performed (ideally within 3 days following subject's decision to withdraw). For all subjects who withdraw, all final safety assessments will be collected as possible regardless of time elapsed since previous visit. In addition to the termination visit, subjects who withdraw early will be contacted within 7 days by study staff via telephone to assess development of new and/or ongoing AEs and concomitant medications. Efforts will be made to recruit subjects to replace any withdrawals before lumbar puncture (or subjects for whom we are unable to get sufficient for analysis) so as to maintain n=6 per group.

Subject's participation may be terminated at the discretion of the investigator. Individuals may be withdrawn for the following reasons:

- Clinically significant adverse events
- Lost to follow-up
- Protocol violations
- Inability to tolerate study medication
- Other

11 Adverse Events (AE) and Serious Adverse Events (SAE)

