7.3.2 Neurological Examination

Neurological examination will be performed at visits 1, 3 or if the subject withdraws early. Any abnormalities noted at Visit 1, will be documented as part of the subject's medical history.

7.3.3 Vital Signs:

Vital signs will be recorded at all three study visits. Diastolic blood pressure will be measured at the disappearance of Korotkoff sounds. Vitals sign will be monitored by clinical staff during screening and lumbar puncture visits of the study.

Serum Glucose will be examined at visit 1 (screening) and visit 3 (safety follow-up). Fingerstick glucose tests will be performed at visit 2 (LP procedure). A blood glucose < 70 mg/dL will be considered clinically significant. The likelihood of peripheral hypoglycemia is low based on numerous clinical trials performed showing no effects of INI on peripheral glucose.

7.3.4 Weight:

Body weight will be measured at all three study visits.

7.3.5 Laboratory Samples:

All the laboratory samples will be drawn independent of fasting or non-fasting status.

When a patient withdraws from the study, samples collected prior to the date of withdrawal may still be analyzed, unless the patient specifically requests that the samples be destroyed or local laws require destruction of the samples. However, if samples have been tested prior to withdrawal, results from those tests will remain as part of the overall research data. Samples will be collected and processed according to the standard procedures. Key planned labs include:

- Basic Metabolic Panel
- Complete Blood Count
- Blood Coagulation Tests

7.3.6 Point-of-Care Glucose Testing:

At Visit 2, the participant will receive a single dose of intranasal insulin administered prior to their lumbar puncture. Point-of-care fingerstick glucose testing will be performed once before the administration of the study drug (baseline glucose reading) and twice after the administration of the drug according to the following schedule:

- (1) 15 minutes after study drug dosing (between the 2nd and 3rd CSF/serum samples are collected)
- (2) 45 minutes study drug dosing (after the final CSF/serum samples are collected)

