12.2 Statistical Analysis of Primary and Secondary Endpoints

Primary Endpoints: We will utilize immunoassay to analyze the CSF samples to determine the levels of Insulin concentration at the specified times. We will graph these values across time for each subject using line graphs. We will also graph the sample average Insulin concentration across time, and at different doses with error bars and report concentrations as mean \pm SE. Finally, the concentrations will be analyzed using common pharmacokinetic measures including the peak concentration (Cmax), time to peak concentration (Tmax), and area under the curve (AUC). This type of analysis is very similar to that done in Dhuria's 2009 publication in the *Journal of Pharmaceutical Sciences*, on which [name] and [name] were co-authors. Similar analysis will be conducted for secondary endpoints.

AEs and SAEs will be categorized and summarized by study group. We will descriptively note if any group was more likely to have experienced a particular AE/SAE or generally experienced more AEs/SAEs throughout the course of the study.

13 Study Conduct Considerations

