13.2.1 Stopping Criteria

Previous research suggests that the incidence of peripheral hypoglycemia in patients given INI at the dosages examined in this trial (40IU and 80IU) is low. However, the study team will obtain point-of-care blood glucose readings before and after administration of the single dose of intranasal insulin and use this information to determine the safety of continued study participation. Although the study team will document the blood glucose readings <70mg/dL as a safety event, levels this low will not necessitate withdrawal/study stoppage. A reading of <54mg/dL will be considered clinically significant regardless of symptoms.

For individual subjects: Study activities will be stopped for participants with Hypoglycemia readings <54mg/dL as measured by point-of-care fingerstick glucose tests. If this value is reached, hypoglycemia rescue measures will be performed, and no additional CSF or blood samples will be collected. If a participant exhibits the following symptoms of dangerous hypoglycemia in the absence of clinically significant value, their participation will be similarly stopped: blurred vision, confusion, slurred speech, cold clammy skin, etc or that requires hypoglycemia rescue measures.

The study team will follow our institution's standard clinical protocol for the treatment of hypoglycemic events. Measures taken to restore glucose levels to >70mg/dL may include oral treatments (e.g., fruit juice or oral glucose gel) as appropriate. If a patient is unresponsive or otherwise not able to take oral treatments, they may be given IV dextrose or intramuscular glucagon.

Participants with glucose levels >54 but less than <70 will not need to be withdrawn based on these values alone. A reading in this range will trigger an ad-hoc glucose test reading for safety monitoring in participants that are otherwise asymptomatic/mildly symptomatic but not requiring rescue measures.

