For dosing cohorts: Participants will be randomized to one of two arms for this study, receiving either a 40IU or 80IU dose of insulin. If two participants in either arm (40IU or 80IU) experience a clinically significant glucose level (<54mg/dL) and/or experience severe/possibly life-threatening symptoms of hypoglycemia as defined in the protocol, the study will be paused and the Data Safety Officer will review data related to these events and recommend a course of action for the study. These options may include, but are not limited to: (1) Adjusting the arm to a lower dose for future enrollees (e.g., reducing the amount from 80IUs to 40IU, or 40IU to 20IUs, etc.), (2) Arm termination, and (3) Study termination.

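### Could replacing participants to keep six per arm hide a dosed participant who was stopped early for low glucose?

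*Combined protocol and SAP*

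**What the plan says.** Section 10.2 has two replacement grounds. The first is plain: "Efforts will be made to recruit subjects to replace any withdrawals before lumbar puncture". The second, in parentheses, adds "or subjects for whom we are unable to get sufficient for analysis) so as to maintain n=6 per group". The noun after the word for adequacy is missing, and no threshold is given.

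Section 13.2.1 sets the individual stopping rule. At a fingerstick below 54 mg/dL, "hypoglycemia rescue measures will be performed, and no additional CSF or blood samples will be collected". For participants with listed symptoms but no low reading, "their participation will be similarly stopped". The arm-level rule begins "If two participants in either arm (40IU or 80IU) experience a clinically significant glucose level" and leads to a pause and review by the Data Safety Officer.

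Section 7.3.6 schedules the first post-dose fingerstick at "15 minutes after study drug dosing (between the 2nd and 3rd CSF/serum samples are collected", and the second at 45 minutes, after all samples. Section 7.3.5 says that, after withdrawal, "samples collected prior to the date of withdrawal may still be analyzed".

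Section 12.2 plans a line graph for each subject, then "We will also graph the sample average Insulin concentration across time, and at different doses with error bars", followed by Cmax, Tmax and AUC, with a similar analysis for serum. It defines no pharmacokinetic set and no rule for a partial profile.

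**The concern.** Read together, these sections let a possible effect of the drug decide who counts among the six. A participant is dosed, has a low reading at 15 minutes, gives no further samples, is judged not to have enough for analysis, and is replaced. The arm table could then read n=6 with no sign that seven people were dosed.

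If low glucose goes with higher systemic uptake, the person lost would tend to have high serum insulin. The arm's mean serum insulin, the secondary endpoint, would then be understated. With six per arm, one person is a sixth of the data. The study is unblinded, and nothing requires adequacy to be judged before assay results are seen. The permissive wording of section 7.3.5 is not a firm safeguard.

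**Working it through.** **No planned figure to reproduce.** The documents give no power, effect size or standard deviation. The only check available is 2 × 6 = 12, which agrees with the accrual target of up to 12.

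**What a stop removes.** Samples are due at 0, 10, 20, 30 and 40 minutes (sections 7.3.11.1 and 7.3.11.2).
- A stop at the 15-minute check leaves 0 and 10 minutes, 2 of 5 samples. The arm then holds 5 × 5 + 2 = 27 of 30 planned CSF samples.
- The 0-minute sample is taken before dosing (section 7.1.2.1), so only the 10-minute value carries information on exposure.
- AUC over 0-40 minutes, Cmax and Tmax cannot be determined for this participant, whichever set is defined.
- The 45-minute check costs no samples. A symptom stop or an ad-hoc reading could fall at other times.

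**How often.** The protocol gives no stop rate, and section 13.2.1 calls hypoglycaemia at these doses low in incidence. Section 1.1.3 does give a related figure: no symptomatic hypoglycaemia in 1092 people.
- One-sided 95% upper limit: 1 − 0.05^(1/1092) = 0.0027, or 0.27%.
- At that rate, at least one in 12: 1 − (1 − 0.0027)^12 = 3.2%. At least one in an arm of 6: 1.6%.
- The 1092 covers symptomatic events at mixed doses. It does not bound silent readings below 54 mg/dL or stops for non-specific symptoms, so higher rates are shown as assumptions.
- At 1%: 1 − 0.99^12 = 11.4%. At 5%: 1 − 0.95^12 = 46.0%.
- Two or more in one arm of 6 at 5%: 3.3%. The case of interest is therefore one stop in an arm, which does not trigger the pause.

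**How large, if the participant's value is left out.** Assume lognormal exposure with CV 30% or 100%, and correlation ρ between exposure and the tendency to be stopped. With log-scale standard deviation σ = √ln(1 + CV²), stop rate p and z = Φ⁻¹(1 − p), the mean among those kept divided by the mean among all is Φ(z − ρσ)/Φ(z).

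| Stop rate | CV 30%, ρ 0.3 to 0.6 | CV 100%, ρ 0.3 to 0.6 |
|---|---|---|
| 0.27% | 0.999 to 0.998 | 0.997 to 0.991 |
| 1% | 0.997 to 0.994 | 0.991 to 0.976 |
| 5% | 0.990 to 0.978 | 0.967 to 0.920 |

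At ρ = 0 the ratio is 1 in every row.

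**Given that one stop happens.** A simulation of 400,000 arms of six removed the person with the highest stop tendency and put in a random newcomer. The average arm mean, relative to truth, was 0.981 and 0.960 (CV 30%, ρ 0.3 and 0.6), and 0.941 and 0.875 (CV 100%). At ρ = 1 it was 0.931 and 0.772. These are averages over arms, not limits. At ρ = 1, 5% of arms moved down by more than 16% (CV 30%) or 49% (CV 100%) relative to their own mean before replacement.

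**What a written rule could recover.** These shifts treat the whole exposure value as lost through the choice of analysis set. After a 15-minute stop that is not so: the 20-40 minute samples were never taken. A rule keeping the participant would restore the 10-minute concentration and nothing later. Averages at 20, 30 and 40 minutes, and the AUC, Cmax and Tmax summaries, would rest on the same complete profiles as before.

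**The case for a change.** The strongest case for a change is that the fix is wording only and the present text permits the omission. Section 10.2 can reach a dosed participant. Section 12.2 does not say whether a replaced person is a subject for the graphs. Section 10.2 requires the reason for withdrawal to be documented, but not shown beside the results. A rule written after the first stop could look data-driven. A descriptive study should still say whose data it describes.

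Much of that stands as a point about completeness: adequacy is undefined, there is no pharmacokinetic set, and a count of those dosed, stopped and replaced by arm would be good reporting.

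It does not show a defect in the analysis. The plan does not say that a replaced participant's data are dropped, and the most natural reading of a graph for each subject includes everyone sampled. The parenthesis follows directly on withdrawals before lumbar puncture and most readily means failed or inadequate collection. Section 7.3.5 permits use of samples rather than excluding them, and the labs it lists are safety panels. Readings below 70 mg/dL are recorded as safety events and adverse events are summarised by group, so the event itself would be visible.

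**Conclusion.** No change is called for. The gap is an unwritten definition, and a competent analyst would fill it by keeping and listing every dosed participant, showing n at each time and marking truncated AUC, Cmax and Tmax as not estimable.

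The avoidable effect is confined to the 10-minute mean when the stop comes at 15 minutes, and it needs an assumed link between stopping and exposure. Treating the whole value as lost, the long-run shift is 0.1-0.9% at a stop rate of 0.27%, and 0.3-8% at assumed rates of 1-5%. A single affected arm could move by more, but most of that loss comes from samples never taken. No direction is shown for CSF insulin, the primary endpoint. The analysis is descriptive, with no test or decision resting on it, and safety reporting is unaffected. The rates of 1-5%, the CVs and the correlations are assumptions; the 0.27% comes from the protocol's own citation and covers symptomatic events only.
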